**Table 2-4 Subgroup analyses**

Subgroup Variable	Primary/Secondary Efficacy Analysis	Selected Safety Analysis
Region	X	X
Stratum (ACEi, ARB, No RASi)	X	X
Age group (< 65 years, ≥ 65 years)	X	X

Subgroup Variable	Primary/Secondary Efficacy Analysis	Selected Safety Analysis
Age group (< 75 years, ≥ 75 years)	X	X
Sex	X	X
Baseline NYHA class group	X	X
Diabetes (history or HbA1c ≥ 6.5%)	X	X
LVEF group (≤ 60%, > 60%)	X	X
Prior heart failure hospitalization	X	

## 2.3 Patient disposition, demographics and other baseline characteristics

### 2.3.1 Patient disposition

#### Disposition for the screening epoch

The number and percentage of patients who completed the screening epoch will be provided. Besides, the primary reason for not completing the screening epoch will be summarized, using the number and percentage of patients not qualifying for such reasons. For any patient who was screened more than once, the data from the last screening will be used in the summary.

The SCR will be used for the above analyses.

#### Disposition for the randomized treatment epoch

The patient status for the randomized treatment epoch will be summarized by treatment group for overall and for each stratum (ACEi, ARB, No RASi), using the number of patients who were randomized, the numbers and percentages of patients who completed the epoch and who discontinued from the study during the epoch; the primary reason for discontinuation from the study during the randomized treatment epoch will be summarized by treatment group for overall and for each stratum (ACEi, ARB, No RASi), using the number and percentage of patients discontinued for such reasons.

The RAN will be used for the above analyses.

#### Disposition for the study treatment

The numbers and percentages of patients who took at least one dose of the study drug, who completed the study treatment and who permanently discontinued from the study treatment will be provided by treatment group, for overall and for each stratum (ACEi, ARB, No RASi); the primary reason for permanent discontinuation from the study drug will be summarized by treatment group, for overall and for each stratum (ACEi, ARB, No RASi), using the number and percentage of patients discontinued for such reasons.

The RAN will be used for the above analyses.

## Protocol deviations

The protocol deviations will be summarized by treatment group and protocol deviation category, for overall and for each stratum (ACEi, ARB, No RASi), using the numbers and percentages of patients with at least one protocol deviation within the protocol deviation category.

The RAN will be used for the above analyses.

## Analysis set dispositions

The numbers and percentages of patients within each analysis set will be provided by treatment group, for overall and for each stratum (ACEi, ARB, No RASi).

In addition, the number and percentage of patients satisfying each criteria leading to exclusion from analysis sets will be provided by treatment group, for overall and for each stratum (ACEi, ARB, No RASi).

### 2.3.2 Background and demographic characteristics

For overall and for each stratum (ACEi, ARB, No RASi), summary statistics will be provided by treatment group for demographics and baseline characteristics, including age, age group (< 65 years, ≥ 65 years), age group (< 75 years, ≥ 75 years), sex, race, ethnicity, category of prior cardiovascular medication, prior heart failure hospitalization, height, weight, body mass index (BMI), body surface area (BSA), waist circumference, hip circumference, sitting pulse, sitting systolic blood pressure (SBP), sitting diastolic blood pressure (DBP), LVEF, atrial fibrillation, atrial flutter, atrial fibrillation/atrial flutter (AF), NT-proBNP, 6MWD, HbA1c, HbA1c group (< 6.5%, ≥ 6.5%), history of diabetes mellitus, diabetes (history or HbA1c ≥ 6.5%), history of hypertension, history of coronary heart disease, NYHA class, KCCQ CSS, region, and stratum (only for overall), where BMI will be calculated as  $\text{weight (kg)} / \text{height}^2 (\text{m}^2)$  from height and weight at screening. If an above variable is scheduled at screening, the scheduled assessment at screening (nominal visit) will be summarized for this variable. If an above variable is scheduled at randomization, the baseline assessment, defined using baseline criteria for efficacy variables (Section 2.1.1), will be summarized for this variable. If an above variable is scheduled at both screening and randomization, both the assessment at screening (nominal visit) and the baseline assessment, will be summarized for this variable.

Continuous variables will be summarized using number of observations, mean, standard deviation, median, minimum, the first quartile (Q1), the third quartile (Q3), and maximum.

Categorical variables will be summarized using frequencies and percentages.

The FAS will be used for the above analyses.

### 2.3.3 Medical history

Any condition entered on the relevant medical history/current medical conditions CRF will be coded using the MedDRA dictionary. Medical history includes heart failure history and other medical history in this study, which are collected at screening. The number and percentage of patients with each medical condition will be provided by treatment group, system organ class (SOC), and preferred term (PT), for overall and for each stratum (ACEi, ARB, No RASi).

The FAS will be used for the above analyses.

## 2.4 Treatments (study treatment, rescue medication, concomitant therapies, compliance)

### 2.4.1 Study treatment / compliance

The study drug administration will be recorded on the CRF page: “Dosage Administration Record – Double-blind Medication” using start date, end date and dispensing level of the study drug. Each pair of start date and end date will be considered as a dosing interval.

For each patient, the dosing intervals will be sorted according to the start date and the end date from the earliest to the latest. It is expected that, for each patient, there should be no gaps and overlaps among dosing intervals, with the exception that, the end date of a dosing interval can be the same as the start date of its next dosing interval, when the patient may take the previous dispensing level in the morning and start a different dispensing level in the evening.

In the presence of gaps or overlaps, data conventional imputation algorithm will be applied to the start date and end date. Detailed algorithm will be provided in the study programming datasets specifications (PDS).

For patients who permanently discontinue from the study treatment, there should be a dosing interval with its start date equal to the date of the permanent discontinuation of the study drug, its end date equal to the study completion/discontinuation date, and its dispensing level equal to “No treatment”.

For each dosing interval, the dispensing level of the study drug will be recorded together with the start date and end date. The dose level and the daily dose (mg/day) are defined based on the dispensing level according to [Table 2-5](#).

**Table 2-5 Dose levels and daily doses of the study drug**

Dispensing Level	Dose Level	Dose			Daily Dose		
		LCZ696	Valsartan	Enalapril	LCZ696	Valsartan	Enalapril
No treatment	0	No Dose	No Dose	No Dose	0 mg/day	0 mg/day	0 mg/day
Dose level 1	1	50 mg bid.	40 mg bid.	2.5 mg bid.	100 mg/day	80 mg/day	5 mg/day
Dose level 2	2	100 mg bid.	80 mg bid.	5.0 mg bid.	200 mg/day	160 mg/day	10 mg/day
Dose level 3	3	200 mg bid.	160 mg bid.	10.0 mg bid.	400 mg/day	320 mg/day	20 mg/day

### Dispensing level, dose level and daily dose at each visit

For a given visit, the visit associated dosing interval is defined as the dosing interval with its start date prior to or equal to the date of visit AND its end date later than or equal to the date of visit; the dispensing level, dose level and daily dose (mg/day) at the visit are defined as the dispensing level, dose level and daily dose (mg/day) for the visit associated dosing interval. In the case that, the visit date is equal to the end date of an earlier dosing interval as well as the start date of a later dosing interval, the later dosing interval will be taken as the visit associated dosing interval.

The dispensing level will be summarized by treatment group and visit, for overall and for each stratum (ACEi, ARB, No RASi), using the number and percentage of patients on each level; the dose level will be summarized by treatment group and visit, for overall and for each stratum

(ACEi, ARB, No RASi), using number of observations, mean, standard deviation, median, minimum, Q1, Q3, and maximum; the daily dose (mg/day) will be summarized by treatment group and visit, for each stratum (ACEi, ARB, No RASi), but not for overall, using number of observations, mean, standard deviation, median, minimum, Q1, Q3, and maximum. The summary will include all scheduled visits in the randomized treatment epoch.

The SAF will be used for the above analyses.

### **Duration of treatment**

The duration (day) of treatment is defined as the date of the last dose of the study drug minus the date of the first dose of the study drug plus one day, regardless of temporary treatment interruption.

The duration (week) of treatment will be converted from the duration (day) of treatment using a factor of 7 day/week, and will be summarized by treatment group, for overall and for each stratum (ACEi, ARB, No RASi), using number of observations, mean, standard deviation, median, minimum, Q1, Q3, and maximum.

The duration (week) of treatment will be categorized into the following categories.

- < 2 weeks
- 2 weeks to < 8 weeks
- 8 weeks to < 16 weeks
- $\geq$  16 weeks

The categorized duration of treatment will be summarized by treatment group, for overall and for each stratum (ACEi, ARB, No RASi), using the number and percentage of patients within each category.

Besides, the overall patient-weeks on-treatment will be provided by treatment group, for overall and for each stratum (ACEi, ARB, No RASi), where the overall patient-weeks on-treatment is defined as the sum of duration (week) of treatment among all patients within the corresponding treatment group and stratum.

The SAF will be used for the above analyses.

### **Duration on each dose level**

For a given dose level, the duration (day) on this dose level is defined as the number of days on this dose level during the period from the date of the first dose of the study drug to the date of the last dose of the study drug. In the case that, the end date of an earlier dosing interval is the same as the start date of a later dosing interval, the day will be counted as 0.5 day on both the earlier dose level and the later dose level. In the case that, the date of permanent discontinuation of the study drug is the same as the date of the last dose the study drug, the day will be counted as 0.5 day on the dose level of the last dose but not counted on dose level 0.

The duration (week) on each dose level will be converted from the duration (day) on this dose level using a factor of 7 day/week, and will be summarized by treatment group, for overall and for each stratum (ACEi, ARB, No RASi).

The SAF will be used for the above analyses.

### **Duration of study drug exposure**

The duration (day) of study drug exposure is defined as the sum of the duration (day) on dose level 1 to 3.

The duration (week) of study drug exposure will be converted from the duration (day) of study drug exposure using a factor of 7 day/week, and will be summarized by treatment group, for overall and for each stratum (ACEi, ARB, No RASi), using number of observations, mean, standard deviation, median, minimum, Q1, Q3, and maximum.

The duration (week) of study drug exposure will be categorized into the following categories.

- < 2 weeks
- 2 weeks to < 8 weeks
- 8 weeks to < 16 weeks
- ≥ 16 weeks

The categorized duration of study drug exposure will be summarized by treatment group, for overall and for each stratum (ACEi, ARB, No RASi), using the number and percentage of patients within each category.

The SAF will be used for the above analyses.

### **Percentage of study drug exposure**

For each patient, the percentage of study drug exposure is defined as the percentage of the duration (day) of study drug exposure out of the duration (day) of treatment.

The percentage of study drug exposure will be summarized by treatment group, for overall and for each stratum (ACEi, ARB, No RASi), using number of observations, mean, standard deviation, median, minimum, Q1, Q3, and maximum.

The SAF will be used for the above analyses.

### **Study treatment permanent discontinuation at each visit**

For a given visit, a patient is considered as permanently discontinued from the study treatment at this visit, if the patient permanently discontinued from the study treatment prior to or on the date of this visit.

For overall and for each stratum (ACEi, ARB, No RASi), the number and percentage of patients who permanently discontinued from the study treatment will be provided for each scheduled visit in the randomized treatment epoch.

### **Mean daily dose and mean dose level**

For each patient, the mean dose level is defined as the weighted mean of the dose level among dose level 0 to 3 using the duration (day) on each dose level as the weight, i.e.,

$$\frac{\sum_{k=0}^3 k \times \text{Duration (day) on Dose Level } k}{\sum_{k=0}^3 \text{Duration (day) on Dose Level } k}$$

The mean dose level will be summarized by treatment group, for overall and for each stratum (ACEi, ARB, No RASi), using number of observations, mean, standard deviation, median, minimum, Q1, Q3, and maximum.

For each patient and each dosing interval, the daily dose is defined based on the dose level and the active study medication for the actual arm according to [Table 1-1](#) and [Table 2-5](#). If there is no active study medication for the actual arm (i.e., the IMT arm in the No RASi stratum), the daily dose is defined as 0 mg/day.

For each patient, the mean daily dose (mg/day) is defined as the weighted mean of the daily dose (mg/day) among dose level 0 to 3 using the duration (day) on each dose level as the weight, i.e.

$$\frac{\sum_{k=0}^3 \text{Daily Dose (mg/day) for Dose Level } k \times \text{Duration (day) on Dose Level } k}{\sum_{k=0}^3 \text{Duration (day) on Dose Level } k}$$

The mean daily dose (mg/day) will be summarized by treatment group, for each stratum (ACEi, ARB, No RASi), but not for overall, using number of observations, mean, standard deviation, median, minimum, Q1, Q3, and maximum.

The SAF will be used for the above analyses.

### **Duration of study exposure**

The duration (day) of study exposure is defined as the date of last visit minus the date of randomization plus one day.

The duration (week) of study exposure will be derived from the duration (day) of study exposure using a factor of 7 day/week, and will be summarized by treatment group, for overall and for each stratum (ACEi, ARB, No RASi), using number of observations, mean, standard deviation, median, minimum, Q1, Q3, and maximum.

The duration (week) of study exposure will be categorized into the following categories.

- < 2 weeks
- 2 weeks to < 8 weeks
- 8 weeks to < 16 weeks
- ≥ 16 weeks

The categorized duration of study exposure will be summarized by treatment group, for overall and for each stratum (ACEi, ARB, No RASi), using the number and percentage of patients within each category.

The SAF will be used for the above analyses.

### **Last recorded dose level**

The last recorded dose level is defined as the dose level for the last dosing interval.

The last recorded dose level will be summarized by treatment group, for overall and for each stratum (ACEi, ARB, No RASi), using the number and percentage of patients on each dose level.

The SAF will be used for the above analyses.

### **Dose down-titration**

A down-titration dosing interval is defined as a dosing interval whose dose level is changed to a lower dose level from its previous dosing interval.

The dose down-titration will be summarized by treatment group, for overall and for each stratum (ACEi, ARB, No RASi), using the number and percentage of patients with at least one down-titration dosing interval.

The SAF will be used for the above analyses.

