5.5.5 Permitted dose adjustments and interruptions of study treatment

For patients who are unable to tolerate the protocol-specified dosing scheme, dose level adjustments and interruptions of study treatment are permitted in order to keep the patient on study drug. The following guidelines should be followed:

- Every attempt should be made to maintain patients at the target study drug dose level throughout the trial. If the patient does not tolerate the target study drug dose level, the investigator can adjust or stop concomitant background medications for comorbid conditions to rectify the situation, before considering to down-titrate to the next lower study drug dose level.

Adjustment of study drug dose level

If despite adjustment of concomitant medications per the guidance provided the situation is not rectified, the investigator may consider down-titrating study drug dose level. As outlined previously, patients in the ACEi and ARB strata take two study medications while patients in the non RASi strata take one study medication. In the ACEi and ARB strata, both study medications must be adjusted simultaneously.

During the randomized treatment epoch, down titration of study drug at any time based on the judgment of the investigator will be allowed according to the safety and tolerability criteria defined in [Appendix 3](#), [Appendix 4](#), and [Appendix 5](#). If down-titration is necessary, the patient should be down titrated to the next lower study drug dose level. If down-titration occurs due to an (S)AE ([Section 7.1](#) and [7.2](#)), then the appropriate reporting guidelines must be followed ([Section 7.2.2](#)). The patient may continue receiving the lower dose level for a recommended period of 1 to 4 weeks before being re-challenged at the next higher dose level. For example, a patient who encounters tolerability problems at the target study drug dose level (dose level 3), should receive study drug at dose level 2 for 1 to 4 weeks at the discretion of the investigator. Then, he/she should be re-challenged with up-titration back to dose level 3. The maximal dose for study medication will be determined by the investigator based upon the patient's individual clinical status.

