### **Time to first down-titration of the study drug**

The time (day) to first down-titration is defined as the start date of first down-titration dosing interval minus the date of first dose plus one day. If no down-titration occurred for the patient, the time (day) to first down-titration will be censored on the date of death (if the patient died), or the date of last visit (if the patient did not die) for the patient.

For overall and for each stratum (ACEi, ARB, No RASi), the time (day) to first down-titration, will be summarized by treatment group, using Kaplan-Meier curves.

The SAF will be used for the above analyses.

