### **Dose interruption**

A dose-interruption dosing interval is defined as a dosing interval whose dose level is 0.

The number and percentage of patients with at least one dose-interruption dosing interval will be provided by treatment group, for overall and for each stratum (ACEi, ARB, No RASi).

The duration of dose interruption is defined as the sum of (the end date minus the start date plus one day) among all dose-interruption dosing intervals.

The number and percentage of patients whose duration of dose interruption is larger than 14 days will be provided by treatment group, for overall and for each stratum (ACEi, ARB, No RASi).

The SAF will be used for the above analyses.

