### **2.5.4 Supportive and sensitivity analyses**

In order to explore the robustness of the MAR assumption on the primary analysis, a sensitivity analysis will be carried out which assesses the situation where the data are missing not at random (MNAR); In particular, the sensitivity analysis will assume that LCZ696 patients who discontinue from the study treatment due to adverse events, death or lack of efficacy will not have adhered to therapy if they had stayed in the study.

Patients who discontinue from the study treatment due to adverse events, death or lack of efficacy are defined as those who discontinued from the study treatment during the randomized treatment epoch, and had the primary reason for discontinuation of study treatment (CRF page: “End of Study Treatment”) specified as “Adverse event”, “Death” or “Lack of efficacy”.

A controlled multiple imputation approach based on pattern mixture models will be applied ([Carpenter and Kenward 2013](#)), whereby all missing data of patients in the LCZ696 group who permanently discontinue study treatment due to: adverse events, death or lack of efficacy, will be assumed to behave like patients in the IMT group after permanent discontinuation and will be imputed based on the data from patients in the IMT group according to the stratum (ACEi, ARB, No RASi).

- For changes from baseline in log(NT-proBNP), for each post-baseline scheduled visit up to Week 12 (Week 4, Week 12), the imputation model will be a linear regression model specified using fully conditional specifications, in which, the response variable will be the

change from baseline in log(NT-proBNP) at the visit; region will be included as a fixed-effect factor; BLNTBNP, change from baseline in log(NT-proBNP) at the closest previous post-baseline scheduled visit (not applicable for Week 4, Week 4 for Week 12) will be included as covariates. For each stratum (ACEi, ARB, No RASi), the imputation model will be fitted separately based on the data from all patients in the IMT group within the stratum.

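### The SAP's down-titration percentage and time-to-first-down-titration curve count temporary and permanent stops as down-titrations, because the rule sets no floor above dose level 0

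*SAP*

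**What the plan says.** All of the rules are in SAP 2.4.1 unless stated otherwise.

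- **Scale.** Table 2-5 gives the dispensing level for no treatment the dose level 0, on the same scale as levels 1 to 3. The mean dose level is a "weighted mean of the dose level among dose level 0 to 3".
- **Down-titration.** A down-titration interval is "a dosing interval whose dose level is changed to a lower dose level from its previous dosing interval". The table reports patients with at least one such interval.
- **Time to first down-titration.** The event time is "the start date of first down-titration dosing interval minus the date of first dose plus one day". If none occurred, the time "will be censored on the date of death (if the patient died), or the date of last visit (if the patient did not die"). The output is a set of Kaplan-Meier curves by arm, overall and by stratum.
- **Interruption.** "A dose-interruption dosing interval is defined as a dosing interval whose dose level is 0".
- **Permanent stop.** For patients who stop for good, "there should be a dosing interval with its start date equal to the date of the permanent discontinuation of the study drug". That interval carries the no-treatment level and runs to the study completion or discontinuation date.
- **Death.** SAP 2.5.4 refers to patients who "permanently discontinue study treatment due to: adverse events, death or lack of efficacy", with the reason taken from the End of Study Treatment page.
- **Protocol 5.5.5.** "If down-titration is necessary, the patient should be down titrated to the next lower study drug dose level". The same section later describes stepping down further, with temporary discontinuation as the end point of that sequence.

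**The concern.** A reader will take a down-titration percentage and a time-to-first-down-titration curve as describing patients who stayed on drug at a lower dose. Under the written rule, a patient interrupted once at level 3 and restarted at level 3 is counted, and so is a patient who stops for good from level 3, although neither ever had a reduced dose.

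Reductions and stops may differ between the arms in different ways, and a pooled figure hides that. It matters because the protocol aims at the maximal tolerated dose for each patient (Protocol 3.1), and these two outputs are the SAP's only dedicated ones on dose reduction by arm. The same permanent stop also appears in the interruption table and in the discontinuation tables.

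**Working it through.** The documents give no figure for down-titration, interruption, discontinuation or on-drug death, so there is no plan figure to reproduce. The check traces the rules, applies them to invented dosing histories, and then shows by assumed rates how the arm comparison could move.

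**1. The chain of rules.** No treatment is level 0. An interruption is a level-0 interval. A permanent stop should have a level-0 interval starting on the discontinuation date. Any interval lower than the one before it is a down-titration. So 3→0→3 and 3→0 both qualify, and the curve takes the start of the level-0 interval as the event date. Nothing in the two down-titration paragraphs excludes level 0. Elsewhere in 2.4.1 the SAP does exclude it: study drug exposure sums levels 1 to 3, and compliance uses positive levels only.

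**2. Invented histories.** First dose is day 1, scheduled end is day 168, and last dose is taken as the day of the stop.

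| History | Rule as written | Level 0 excluded, nothing else changed | Full change (see fix) |
|---|---|---|---|
| 3→2 on day 60 | event, day 60 | event, day 60 | event, day 60 |
| 3→0 on day 60, back to 3 on day 70 | event, day 60 | censored, day 168 | censored, day 168 |
| 3→0 on day 60, restart at 1 on day 70 | event, day 60 | censored, day 168 | event, day 70 |
| Permanent stop day 60, followed to day 168 | event, day 60 | censored, day 168 | censored, day 60 |
| Permanent stop day 60, death day 120 | event, day 60 | censored, day 120 | censored, day 60 |
| Death on drug day 100, level-0 row entered | event, day 100 | censored, day 100 | censored, day 100 |
| Same death, no level-0 row | censored, day 100 | censored, day 100 | censored, day 100 |
| Completer, no change | censored, day 168 | censored, day 168 | censored, day 168 |

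Three things follow. Stops are events as written. The same death is an event or is censored according to whether a row was entered. Excluding level 0 alone is not enough: a permanently stopped patient would stay at risk until the last visit although no reduction can then occur, and a restart at a lower level would be missed.

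**3. The interruption table.** It takes every level-0 interval, so it also takes permanent stops. For the stop on day 60 followed to day 168, the SAP's interruption duration is 168 − 60 + 1 = 109 days. This patient therefore also enters the count of interruptions longer than 14 days.

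**4. Possible effect on the arm comparison.** Let r be the proportion with a true reduction to a lower positive level and s the proportion ever moving to level 0. If the two are independent, the reported proportion is 1 − (1 − r)(1 − s). All rates below are assumptions.

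| r (arm A vs B) | s (A vs B) | Reported, A | Reported, B | True ratio → reported ratio |
|---|---|---|---|---|
| 15% vs 8% | 12% vs 12% | 1 − 0.85 × 0.88 = 25.2% | 1 − 0.92 × 0.88 = 19.0% | 1.88 → 1.32 |
| 15% vs 8% | 18% vs 18% | 1 − 0.85 × 0.82 = 30.3% | 1 − 0.92 × 0.82 = 24.6% | 1.88 → 1.23 |
| 12% vs 10% | 18% vs 10% | 1 − 0.88 × 0.82 = 27.84% | 1 − 0.90 × 0.90 = 19.00% | 1.20 → 1.47 |
| 12% vs 10% | 10% vs 14% | 1 − 0.88 × 0.90 = 20.8% | 1 − 0.90 × 0.86 = 22.6% | 1.20 → 0.92 |

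Independence is the weak assumption. If every stop followed a reduction in the same patient, the reported proportion would equal r and the percentage table would not change at all.

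**The case against.** The strongest defence is that level 0 belongs on the scale by design. The SAP averages over levels 0 to 3 and reports the last recorded level with no floor, and Protocol 5.5.5 presents temporary discontinuation as the last step of stepping down. On that reading, censoring at the last visit is coherent, because stopped patients already have their event. Other outputs also help a reader separate the components: dose level by visit, time on each level, permanent discontinuation by visit and by reason, and adverse events leading to dose adjustment or interruption.

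Part of this stands. The rules are coherent as a composite, and counting temporary stops is arguable. Permanent stops have no such support. Protocol Appendices 3, 4 and 5 present reducing and stopping as different actions, and SAP 2.8.1 records dose reduced, drug interrupted and drug withdrawn as different answers. The adverse-event summary does not fill the gap either: it pools reductions, increases and interruptions, and covers only changes made for adverse events.

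A reader might infer more than the documents support, on three points.

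- *That on-drug deaths are certainly events.* Death is a listed reason on one CRF page, while the level-0 row comes from the Dosage Administration Record. The SAP does not say that a death creates such a row.
- *That the curve's censoring rule contradicts its event rule.* Censoring at death applies only where no down-titration occurred, so it says nothing about a patient who already has an event.
- *That the pooling always dilutes a difference.* The assumed rates above show movement in either direction.

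**Conclusion.** The concern holds as a fault of derivation and labelling. As written, the down-titration percentage and curve show any reduction or stop. For temporary and permanent stops this follows directly from the SAP text, provided that the dosing records are completed as the SAP expects. For deaths on drug it depends on data entry, which is itself a gap in the rule.

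The size cannot be computed from the documents; the ratios above show only that dilution, inflation and reversal are all possible. The effect is confined to descriptive outputs on the safety set. No hypothesis test, alpha level, power figure or efficacy estimate is touched.

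**What to change.** Change three paragraphs of SAP 2.4.1 before database lock.

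1. **Dose down-titration.** Count an interval only if it is at dose level 1 or 2 and lower than the most recent earlier positive level. A 3→0→1 sequence then counts at the restart.
2. **Time to first down-titration.** Censor at last dose for permanent discontinuation, or at death. Alternatively, show a cumulative incidence with permanent discontinuation and death as competing events. Either way, deaths no longer depend on whether a row was entered.
3. **Dose interruption.** Exclude the permanent-discontinuation interval, so that reductions, interruptions and permanent stops are reported separately.

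If the sponsor wants the composite, it can stay as an additional output labelled *first dose reduction or stop*.

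The cost is a few sentences of SAP wording and a small programming change. The reported down-titration rate will fall. Censoring at a permanent stop may be informative, since patients may stop because they do not tolerate the drug; the competing-event version avoids that.
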